GALDERMA EST. 1981	Title 43QM2106 Clinical Study Protocol – QM1114 – GL	Doc id MA-49290
------------------------------	--	---------------------------

Visit	Visit 1	Visit 2	Visit 3	Visit 4	Visit 5	Visit 6	Visit 7	Visit 8	Visit 9	Visits 10-14	Visit 15
1 month = 4 weeks All visit windows are calculated from Baseline/Day 0		Day 0 Baseline ¹	Day 1	Day 2	Day 3	Day 4	Month 1	Month 3	Month 6	Months 7-11	Month 12/ EOS/ET ²
Window	(≤ 2 weeks of Visit 2)						(± 5 days)	(± 5 days)	(± 5 days)	(± 5 days)	(± 5 days)
CCI											

Abbreviations:EOS = End of Study; ET = Early Termination; **CCI**GAIS = Global Aesthetic Improvement Scale; **CCI**

1. Screening and baseline visits may be performed on the same day. If performed on the same day, study activities should only be completed once (i.e., UPT, subject and investigator GL severity assessments, focused physical exam, vital signs, and inclusion/exclusion criteria review).
2. If the subject withdraws before the final visit the assessments at Month 12/EOS/ET should be completed, if possible.
3. Includes date of birth, gender, race, ethnicity, height, weight, Fitzpatrick skin type.
4. For previous toxin treatments, capture; brand, area(s) treated, and date(s) on the previous medications/procedures form.
5. Females of childbearing potential.
6. Post-baseline, events suggestive of remote spread of toxin are also considered while doing clinical evaluations based on the subject's symptoms and signs. Directed questioning and examination will then be performed as appropriate.
7. Performed pre-treatment.
8. Vital signs include blood pressure, heart rate and respiratory rate. Vital signs are taken seated, after approximately 10 min rest.
9. Only at select sites.
10. Performed pre- and post-treatment.
11. Subject will make his/her assessment independently of the investigator's assessment.
12. Performed at month 9 only
13. Part 1 to be completed post-treatment at baseline (Visit 2) and Part 2 to be completed at Month 1 (Visit 7).

CONFIDENTIAL
Page 19 of 86

GALDERMA <small>EST. 1981</small>	Title 43QM2106 Clinical Study Protocol – QM1114 – GL	Doc id MA-49290
---	---	----------------------------------

LIST OF ABBREVIATIONS AND DEFINITIONS OF TERMS

Abbreviation/Term	Definition
°C	Degrees Celsius
AE	Adverse event
BCOP	Bovine corneal opacity and permeability
BOCF	Baseline observation carried forward
BoNT	Botulinum toxin
BoNT-A	Botulinum toxin type A
CFR	Code of Federal Regulations
CM	Centimeter
CMH	Cochran Mantel Haenszel

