Due to the COVID-19 pandemic, the feasibility and immediate necessity of starting a new clinical trial should be critically assessed and additional risks to trial participants should be addressed. Thus, a risk benefit assessment of the impact of COVID-19 potentially affecting trial participants and COVID-19 related measures affecting clinical trial conduct will be performed before the study starts to decide if the study can start or if it needs to be postponed. If the conclusion of the assessment is that the risk benefit is currently negative the study will not start until the outbreak is under control with a substantially reduced risk for subjects being infected by COVID-19, as guided by relevant research and local and international health authorities' guidelines and regulations. Measures to minimize the risk of exposure to COVID-19 for study subjects include, but is not limited to, replacing site visits with telephone call visits, replacing live assessments with remote digital assessments, postponing site visits and cancellation of site visits not needed for evaluation of the primary endpoint.

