5.5 Procedures/Reasons for Subject Discontinuation

An investigator may decide to discontinue a subject from the clinical study for safety reasons.

Although the importance of completing the entire clinical study should be explained to the subject by the clinical study personnel, any subject is free to discontinue participation in this clinical study at any time and for whatever reason, specified or unspecified, and without any prejudice. No constraints are to be imposed on the subject, and when appropriate, a subject may be treated with other conventional therapy when clinically indicated.

When a subject does not complete the clinical study, he/she will be fully assessed, if such assessment is possible. The procedures designated for the Month 12/ Early Termination (ET) visit should be completed for all subjects discontinuing the clinical study and the appropriate eCRF should be completed.

All discontinuations and the reason for discontinuation are to be documented by the investigator on the exit form. For discontinuation due to an AE, the AE form is to be completed. The investigator should also ensure that the subject receives suitable therapy for the AE.

Potential reasons for discontinuation are listed below:

- **Adverse Event:** Complete an AE form.
- **Withdrawal by Subject:** Includes consent withdrawal, subject relocation, schedule conflicts, etc. Explain the reason for withdrawal in the comment section of the eCRF exit form.
- **Lost to Follow-up:** Confirmed with two documented phone calls and a certified letter (delivery receipt requested) without answer. Explain in the comment section of the eCRF exit form.

 EST. 1981	Title 43QM2106 Clinical Study Protocol – QM1114 – GL	Doc id MA-49290
---	--	---------------------------

- **Other:**

This category is to be used for a subject who discontinues due to a reason other than as specified in the predefined categories above. Explain the reason for discontinuation in the comment section of the eCRF exit form.

A subject who has been randomized and assigned a kit number/randomization number cannot be replaced by another subject if he/she discontinues the clinical study for any reason. Additional subjects could be enrolled (randomized/assigned to treatment) in order to attain the number of evaluable subjects.

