7.1.2 Subject Diary Card

Subjects will be asked to record their assessment of study treatment response in a diary card on Days 0 through 7 post-treatment. They will be asked to respond “yes” or “no” to the following question:

“Since being injected have you noticed an improvement in the appearance of your glabellar lines (lines between your eyebrows) when you frown?”

Subjects are to complete the diary card daily, starting on the day of treatment (Day 0), and return the diary to study center at their Month 1 visit.

CCI

[figure not shown]

[figure not shown]
[figure not shown]
Effective date: 2022-03-21 13:08

Effective

Version: 3.0

CCI

 EST. 1981	Title 43QM2106 Clinical Study Protocol – QM1114 – GL	Doc id MA-49290

CCI
 		

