7.2.4.1 Definitions

7.2.4.1.1 Adverse Events

According to International Council for Harmonisation (ICH) E2A,¹⁵ an AE is any untoward medical occurrence in a patient or a clinical investigation subject administered a pharmaceutical product and which does not necessarily have a causal relationship with this treatment. An AE can therefore be any unfavorable and unintended sign (including an abnormal laboratory finding), symptom, or disease temporally associated with the use of a medicinal (investigational) product, whether or not related to the medicinal (investigational) product.

Thus, any new sign, symptom or disease, or any clinically significant worsening of an existing sign, symptom or disease (including new episodes of a chronic disease [e.g., hay fever, allergy]) compared to the condition at the first visit, should be considered as an AE. Lack of efficacy is not considered as an AE.

Notes:

- There should be an attempt to report a diagnosis rather than the signs, symptoms or abnormal laboratory values associated with the report of an AE. However, a diagnosis should be reported only if, in the investigator's judgment, it is relatively certain. Otherwise, symptoms, signs, or laboratory values should be used to describe the AE.
- Pregnancy is not to be considered as an AE; however, is an important medical event that must be monitored as described in Section 7.2.4.2.3.

 EST. 1981	Title 43QM2106 Clinical Study Protocol – QM1114 – GL	Doc id MA-49290
---	--	---------------------------

- The effects of all BoNT products may spread from the area of injection to produce symptoms consistent with BoNT effects. These symptoms have been reported hours to weeks after injection. Remote spread of toxin that affects swallowing and breathing can be life threatening, and there have been reports of death. The risk of symptoms is increased in subjects who have underlying conditions (e.g. disorders of the neuromuscular junction) that would predispose them to these symptoms. BoNT is contraindicated in individuals with known hypersensitivity to any BoNT preparation or to any of the components in the formulation.

7.2.4.1.2 *Treatment Emergent Adverse Event*

A TEAE is an event that emerges during or after treatment, having been absent pre-treatment, or worsens relative to the pre-treatment state.

7.2.4.1.3 *Serious Adverse Events*

A SAE is any untoward medical occurrence that at any dose:

- Results in death,
- Is life-threatening,

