5. CCI [REDACTED]
6. CCI [REDACTED]
(Section 7.1.7).
7. Review GAIS completion instructions with the subject. Subject to complete the GAIS (Section 7.1.1).
8. CCI [REDACTED] (Appendix 1).
9. CCI [REDACTED] (Appendix 2).
10. CCI [REDACTED] (Appendix 3).
11. CCI [REDACTED] (Appendix 4).
12. Obtain the subject's vital signs (blood pressure, heart rate, and respiratory rate). Vital signs are to be taken seated after 10 minutes rest (Section 7.2.2).
13. CCI [REDACTED] (Section 7.1.8 and Appendix 5).
14. Investigator to perform a FPE (Appendix 7).
15. Exit the subject from the study.

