1.3.2 Subject Diary Card

Subjects will be asked to record their assessment of study treatment response in a diary card on Day 0 (baseline post-treatment) through Day 7. They will be asked to respond “Yes” or “No” to the following question:

- *“Since being injected have you noticed an improvement in the appearance of your glabellar lines (lines between your eyebrows) when you frown?”*

Subjects will complete the diary card daily, starting on the day of treatment (Day 0), and will return the diary to study site at their Month 1 visit.

For each subject, time, in days, to onset of treatment response will be computed. A flag will be created to determine the diary date of when the subject first answers 'Yes' to "Since being injected have you noticed an improvement in the appearance of your glabellar lines (lines between your eyebrows) when you frown?" Time, in days, to onset of treatment response will be calculated as follows:

$$\text{Number of days to onset} = \text{Date of Diary Flag} - \text{Date of Day 0}$$

Subjects who never notice an improvement will be censored at Day 7. Subjects dropping out before noticing improvement will also be censored at Day 7 or date of withdrawal, whichever comes first. Subjects who never return their diary will be censored on Day 7.

[figure not shown]
CCI

Sponsor: *Galderma*

Protocol Number: *43QM2106*

Plan Version: *V1.0*

CCI

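### A subject who formally discontinues before Month 1 but still accepts contact has no route to give the Month 1 GAIS or hand in the onset diary; the rating is scored 'No Change' and the diary is censored at Day 7

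*Protocol*

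**What the plan says.** **Exit route.** Protocol 5.5 defines the category of withdrawal by the subject as follows: "Includes consent withdrawal, subject relocation, schedule conflicts, etc". For the exit itself it states: "The procedures designated for the Month 12/ Early Termination (ET) visit should be completed for all subjects discontinuing the clinical study". Footnote 2 to Table 2 agrees: "If the subject withdraws before the final visit the assessments at Month 12/EOS/ET should be completed, if possible". Neither place distinguishes a subject who can no longer come to the site from one who refuses further contact.

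**GAIS.** The Month 12/ET list in Protocol 8.1.9 does include the rating: "Review GAIS completion instructions with the subject. Subject to complete the GAIS". SAP 2.1.1 tabulates data under the visit recorded on the eCRF, even when that visit is out of window. SAP 1.3.1 lets only a response at the Month 1 visit make a subject a Month 1 responder. Protocol 9.1.5 and SAP 2.4.2 replace a missing Month 1 GAIS with 'No Change' in the primary analysis.

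**Diary.** Subjects complete it on Days 0 to 7 and are told to "return the diary to study center at their Month 1 visit" (Protocol 7.1.2, repeated in 8.3). The collection step is in 8.1.5 (Month 1) and not in 8.1.9 (Month 12/ET), and Table 2 marks collection at Visit 7 only. SAP 1.3.2 says: "Subjects dropping out before noticing improvement will also be censored at Day 7 or date of withdrawal, whichever comes first". Its next sentence censors a diary that is never returned at Day 7. SAP 2.4.5.1 says instead that missing observations for secondary endpoints stay missing.

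**Remote contact.** Protocol 1.3 and SAP 2.1.1 allow "replacing site visits with telephone call visits, replacing live assessments with remote digital assessments", but only as a COVID-19 measure.

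**The concern.** Study treatment is one injection on Day 0. Leaving the visit schedule afterwards does not interrupt treatment, so the Month 1 state of the glabellar lines still exists and the subject can still report it. The GAIS is a single self-rated question. For a subject who has moved away but would take a telephone call, 'No Change' replaces an answer that could have been obtained.

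The diary problem is similar. It is complete by Day 7, about three weeks before its only planned collection. A subject who writes yes on Day 2 and discontinues on Day 10 has already supplied the onset endpoint, but no step retrieves the card. The dropout rule in SAP 1.3.2 depends on whether the subject had noticed improvement, and only that card shows it.

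There is a smaller safety aspect. The protocol says of toxin-spread symptoms: "These symptoms have been reported hours to weeks after injection". After an early ET visit no planned contact asks about new events.

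**Working it through.** **1. Follow one early leaver through the text.** Take a subject who writes yes on Day 2 and discontinues on Day 10 because of relocation.

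- Protocol 5.5 and 8.1.9: ET procedures on Day 10, if possible. The GAIS is asked and filed under Visit 15.
- SAP 1.3.1 and 2.1.1: no Month 1 visit, hence no Month 1 rating. No rule maps an ET rating to Month 1.
- SAP 2.4.2: Month 1 set to 'No Change', a non-responder.
- Protocol 8.1.9 and Table 2: no diary collection at ET.
- SAP 1.3.2: if the card stays unreturned, the subject is censored at Day 7, as if no onset had been reported.
- SAP 2.4.5.1: the same subject would instead be left missing.

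Table 2 sets one month at four weeks, so the Month 1 window is 28 ± 5, Days 23 to 33. An ET rating taken inside those days is still not assigned to Month 1 by any rule.

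**2. Do the planned sensitivity analyses recover the rating?** No.

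- The observed-case analysis drops the subject.
- The per-protocol population requires a completed Month 1 visit (SAP 2.2).
- Multiple imputation conditions on treatment group and GAIS at earlier scheduled time points (SAP 2.4.2), so an ET rating filed under Visit 15 is not an input.

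**3. Figures in the plan.** The plan states no figure on this point. The planned size is 90 active and 30 placebo (Protocol 9.2). Its historical data, assumptions and calculation are redacted, so 120 cannot be reproduced. The one open figure does reproduce: 120/0.90 = 133.3, rounded up to the stated 134 screened.

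**4. Primary rate.** One true responder scored 'No Change' costs 1/90 = 1.1 points in the active arm or 1/30 = 3.3 points in the placebo arm. Now assume 2 to 5 active subjects leave and true response is 90%: 2/90 × 0.90 = 2.0 points and 5/90 × 0.90 = 5.0 points. For placebo, with an assumed 10% response, one leaver costs 1/30 × 0.10 = 0.3 points on average.

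With the same share d lost in both arms, and loss unrelated to response, each rate is multiplied by (1 − d), and so is the difference. At assumed rates of 90% and 10%:

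| d | Difference (points) |
|---|---|
| 0 | 80.0 |
| 3% | 77.6 |
| 5% | 76.0 |
| 10% | 72.0 |

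**5. Power.** This uses an unstratified normal-approximation test of two proportions, 30 against 90, two-sided 5%. Power stays above 99.9% for assumed rates from 95/5 to 80/20 with d up to 10%. At 70/30 it falls from 98.0% to 94.6% at d = 10%.

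**6. Onset.** Assume 90% truly report onset by Day 7 and a share f of diaries is never collected, unrelated to onset. Those subjects stay at risk through Day 7 without an event, so the Kaplan-Meier estimate at Day 7 is 0.90 × (1 − f). Under SAP 2.4.5.1 they drop out and the expected estimate stays at 90%.

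| f | SAP 1.3.2 (censor at Day 7) | SAP 2.4.5.1 (leave missing) |
|---|---|---|
| 3% | 87.3% | 90% |
| 5% | 85.5% | 90% |
| 10% | 81.0% | 90% |

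**The case against.** **Discontinuing is not the same as missing visits.** This stands. Protocol 5.5 lists reasons for a discontinuation that has already happened and does not require anyone to be discontinued for a missed visit. A late Month 1 visit is still tabulated as Month 1. A reader might infer that the consecutive-day visits on Days 0 to 4 themselves cost primary data; nothing in the documents supports that. The point applies only to formal exits before Month 1.

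**The ET visit collects a good deal.** This also stands. A reader might infer that the rating and the adverse event assessment are wholly lost. They are not: ET includes the GAIS, the open adverse event question and the focused physical examination, whose form covers local and remote toxin spread. Related events are followed until resolved or stable (7.2.4.2.1), and investigators are asked to pass on relevant safety information learned later (7.2.4.1.5). What is missing is a rating usable as Month 1 and a planned question about events arising after an early exit.

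**Nothing forbids handing in the diary at ET.** True, and 5.5 asks for a full assessment where possible. But the content given to that assessment is the ET list, which has no diary step. Redaction does not explain the gap: the diary rows in Table 2 and the collection step in 8.1.5 are readable.

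**'No Change' is prespecified, applies to both arms and has sensitivity analyses.** It is a defensible rule for data that cannot be obtained. It does not justify leaving obtainable data uncollected, and those analyses cannot restore the rating.

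**A leaver may receive other treatment before Month 1.** 5.5 permits conventional therapy when indicated. The SAP already answers this: its primary estimand (2.4.4) uses the observed response after prohibited treatment.

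**A remote rating is not identical to an on-site one.** It may lack the baseline-photograph review. That review is optional under 7.1.1, and the difference can be tested.

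**Conclusion.** The gap is real and narrow. It concerns subjects who formally discontinue before Month 1 without refusing further contact. For them an obtainable Month 1 rating becomes an assumed non-response. A completed diary has no planned collection point, and the SAP gives two incompatible rules for it when it is not returned. Data from subjects who truly withdraw consent to contact cannot be recovered and are outside the point.

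The size cannot be established: the readable text gives no pre-Month 1 dropout rate and no expected responder rates. Only the 1.1 points per active responder lost (3.3 for placebo) follows from the plan's own numbers. The 2.0 to 5.0 point range, the shrinkage of the difference and the onset figures all rest on assumed rates. If loss is equal across arms, the primary difference is biased towards zero, and the Day 7 rule pulls reported onset down.

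A reader might infer that the primary test is in danger. The calculation does not support that: at large assumed effects power hardly changes. The case for acting is that the estimates improve at very little cost.

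**What to change.** 1. **Diary.** In Protocol Table 2 and 8.1.9, add collection of the diary card at the ET visit if it has not already been returned, with return by mail as an alternative. Reconcile SAP 1.3.2 with 2.4.5.1 so that one rule governs an unreturned diary.
2. **Exit categories.** In Protocol 5.5, separate stopping visits from withdrawing consent to further contact. For the former, before Month 1, obtain the GAIS and the open adverse event question by telephone or other remote means within the Month 1 window, and record them as Month 1.
3. **Filing rule.** State in the SAP that an ET GAIS taken inside the Month 1 window is filed as Month 1.
4. **Analysis.** Use these ratings as observed in the primary analysis, in line with the estimand's handling of prohibited treatment. Flag them and repeat the primary analysis without them.

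The cost is a short protocol amendment, two SAP edits, and one remote contact for each such leaver. Sites already telephone subjects before declaring them lost to follow-up. The downside is that a few Month 1 ratings would be remote and might lack the optional photograph review; the repeat analysis in item 4 shows whether that matters.

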6. CLINICAL SUPPLIES

Details of the drug composition and excipients are provided in the current QM1114-DP IB.¹²

6.1 Clinical Supply Identification and Use

6.1.1 QM1114-DP

The investigational product (QM1114-DP) will be supplied as a sterile solution for injection containing the drug substance, QM1114-DS. The drug substance is a BoNT Type A. QM1114-DS is diluted in a buffer solution.

At the baseline visit, a total volume of 0.5 mL of QM1114-DP will be administered in 5 equal aliquots of 0.1 mL each per the blinded randomization assignment.

CCI

6.1.2 Placebo

Placebo will be supplied as a buffered solution for injection containing only the buffer solution of QM1114-DP; placebo does not contain active drug substance.

At the baseline visit, a total volume of 0.5 mL of placebo will be administered in 5 equal aliquots of 0.1 mL each per the blinded randomization assignment.

The placebo product should be stored at the recommended temperature (between 2°C and 8°C, 36 °F – 46 °F). The placebo product should not be frozen and should be protected from light.

 EST. 1981	Title 43QM2106 Clinical Study Protocol – QM1114 – GL	Doc id MA-49290
---	--	---------------------------

6.1.3 Study Products(s) Description

Table 3 Description and Usage of the Study Products(s)

	Investigational product	Reference product
Name of drug substance	QM1114-DS	N/A
Internal Code	QM1114-DP	Placebo
Pharmaceutical Form	Solution for injection	Solution for injection
Concentration	100 U/mL, buffered solution	N/A, buffer solution
Buffer composition	CCI	
Packaging	Glass vial. Fill volume 1.5 mL	Glass vial. Fill volume 1.5 mL
CCI		
Dosage	50 U 0.5 mL total 0.1 mL per injection point	N/A 0.5 mL total 0.1 mL per injection point
Route	Intramuscular injection	Intramuscular injection
Dose regimen	Single treatment at baseline visit	Single treatment at baseline visit
Location of treated area	Glabellar region	Glabellar region

6.1.4 Subject Identification Number

Each study participant who has signed the Informed Consent Form (ICF) will be entered into the eCRF system and a subject identification number (SIN) will be assigned via the eCRF system. For the duration of the study, the subject will be identified using the subject number for all documentation and discussion.

Subject numbers will consist of the study center number followed by a consecutive number starting with 001 at each center. The subject numbers shall be allocated in ascending sequential order within each center. If a subject is deemed not eligible for the study participation, the reason for screen failure should be specified. A screen failure cannot be re-screened.

A log/listing should be maintained by each site for all subjects who have signed the ICF. There should be sufficient information to link the eCRF to a study subject's source documents and medical records.

